#### CS2.1 Research Protocol Abstract:

The majority of patients with multiple sclerosis (MS) suffer from constipation and/or fecal incontinence ("anorectal dysfunction"), and these difficulties are often ranked as negatively impactful on quality of life as impaired mobility. Despite the significant clinical burden of these symptoms, there remains very little research to support specific therapeutic options in managing anorectal dysfunction in MS patients. To address this gap in knowledge, we propose to establish the efficacy of a standardized, cost-effective, and easily implemented bowel regimen to treat anorectal dysfunction in patients with MS.

Specifically, this double-blind, randomized placebo controlled study will determine the impact of adding the regular administration of rectal suppository laxatives (e.g., a "timed rectal evacuation" strategy) on MS patients' subjective assessment of bowel symptoms. The "timed rectal evacuation" aspect of a bowel regimen has never been rigorously studied, but it could have a major clinical impact. In our study, patients with MS will receive oral laxatives or anti-diarrheal agents to normalize stool form (as indicated), and then be randomized to receive either placebo or bisacodyl 10 mg rectal suppositories administered every other day for 4 weeks. Patients also will undergo tests of anorectal function (per routine clinical practice) and standardized questionnaire assessments of bowel symptoms and their impact on quality of life. We will use this information to try to predict which groups of patients benefitted from the intervention. This proposal will significantly advance MS care and management by developing the evidence to support a simple and effective clinical treatment algorithm for anorectal dysfunction in the MS population.

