# AIM 1: Determine the impact of timed rectal evacuation on anorectal dysfunction in MS patients

We will conduct a four week, single-center, randomized, double-blind placebo controlled clinical trial designed to assess the efficacy of timed rectal evacuation in improving the subjective global assessment of bowel symptoms in a cohort of patients with mild-to-moderate severity MS disease. Patients will be randomized 1:1 to administer either placebo or bisacodyl 10 mg rectal suppositories every other day during the 4 week trial. The primary endpoint will be the change in patients' rating of bowel symptom severity (10 point rating scale) at end of 4 weeks compared to baseline values. We will define an adequate treatment response as greater than a 30% reduction in symptom severity using an intention-to-treat analysis.

AIM 2: Determine the predictors of treatment response and impacts on quality of life

We plan to collect information on the patients' assessed severity of baseline and treatment-associated anorectal dysfunction, their impact on quality of life, as well as daily bowel diaries. Patients also will undergo anorectal sensory and manometric testing as a part of their routine clinical care. Enrolled patients that complete the study will be assessed for study medication compliance. All of these measures will be used to explore factors that are associated with treatment response. Changes in assessments of anorectal dysfunction-related quality of life will serve as key secondary end-points.

This proposal will significantly advance MS care and management by developing the evidence to support the adoption of a simple, safe, and cost-effective clinical treatment algorithm for anorectal dysfunction in the MS population. This paradigm for anorectal dysfunction management could be applicable to a majority of MS patients, and the treatment algorithm could be introduced to patients by nurses or mid-level clinical providers during points of routine MS patient care. Importantly, the treatment could be effectively accomplished by most patients and their caregivers at home. The findings of this investigation could also have a broader influence on care models for anorectal dysfunction associated with a range of other neurological illnesses, such as Parkinson's Disease, ALS, or stroke.

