Finally in Phase 3, after the 4 week study period, patients will meet with the study coordinator to collect unused study medication and completed bowel diaries, and then undergo final reassessments of bowel dysfunction severity and QOL measures. This process could take up to 1 hour. After the questionnaires are completed, patients and the PI/Co-PI will be debriefed (i.e. study arm allocation will be revealed) before having a routine followup clinic visit (continuity of care).

- 1) The study coordinator will identify and screen potential study subjects (by accessing the "UPMC Multiple Sclerosis and Related Disorders Registry" (PRO12010609) to identify prospective subjects), coordinate the informed consent process with the PI/Co-PI, collect intake questionnaires, and provide instruction on bowel diaries (Phase 1). The coordinator will schedule referrals for anorectal function testing and follow-up DDC visit, and contact patients during the 4-week trial period to verify compliance. Finally, the coordinator will collect bowel diaries and remaining medications at study end, administer study exit questionnaires, and then debrief subjects and the PI/Co-PI once the blind is broken (Phase 3).
- 2) DDC GI nursing staff routinely performs HRAM studies and will do so in this study. The PI/Co-PI will be involved in clinical care and recommendations both during Phase 2 and Phase 3 (and beyond).
- 3) MS Physicians will be involved in initial identification of potential subjects and all MS-related continuity of care.
- 4) Falk Pharmacy serves UPMC for clinical trials, and staff will ensure the 1:1 randomization and distribution of either twenty placebo or biscodyl 10 mg rectal suppositories (used every other day over 4 weeks during the study period). Falk Pharmacy staff is experienced in running clinical trials and maintaining double-blind study conditions between subjects and investigators. Patients will receive a slight excess number of suppositories in order to assess study medication compliance at trial end.

STUDY MEASURES: We plan to obtain the following information from all enrolled patients:
1) Primary Patient-Reported Outcome Measure: "Using a scale of 1 to 10 (1 being no problem and 10 being maximally impactful symptoms), how would you rate the severity of your bowel symptoms over the past 2 weeks?"

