#### SECONDARY END POINTS:

1) Daily Bowel Diaries – patients will record the consistency (Bristol Stool Scale, 1-7), number of bowel movements (BM), and occurrence of any fecal incontinence (FI) episodes each day. This data will be used to abstract BM and FI weekly frequency, as well as the mean change in stool consistency during the study period.

- 2) Patient Assessment of Constipation Symptom Questionnaire (PAC-SYM)
- 3) Fecal Incontinence Severity Index (FISI)
- 4) Patient Assessment of Constipation QOL (PAC-QOL)
- 5) Rockwood Fecal Incontinence Quality of Life Scale (FIQL)
- 6) SF-36 health status questionnaire
- 7) Study Medication Compliance
- 8) Anorectal Sensory and High Resolution Anorectal Manometry Testing: First sensation of rectal filling, urgency, and pain, basal anal resting pressure, voluntary anal squeeze pressure, and the rectal-anal inhibitory reflex (RAIR) to rectal distention and simulated strain, as well as the ability to evacuate a 50 cc volume rectal balloon within one minute.
- 2.18 Describe the statistical approaches that will be used to analyze the study data.
  - \* Addressed below:

Categorical data will be analyzed using Fisher's Exact tests for differences in proportions. Continuous data will be analyzed using Student's t-tests to detect differences in group means, with Bonferroni correction for multiple comparisons. We will use logistic regression to determine the factors that predict treatment responses.

A p<0.05 will be used as the threshold for statistical significance in all cases.

POWER ANALYSIS/SAMPLE SIZE: It is generally regarded that a 3-point reduction represents a clinically meaningful change using such a 10 point scale, and similar research studies using patient-reported outcomes have reported standard deviations ranging around ~2.5 points. However, we do not have baseline data to estimate variance, and thus we took a conservative estimate with an expected standard deviation of 4 points. Given these assumptions, we will need 28 patients in each study arm to detect at least a 30% reduction in symptom severity, with a power of 0.80, alpha=P<0.05 in a two-tailed analysis.

[reviewer notes-]

- 2.19 Will this research be conducted in (a) a foreign country and/or (b) at a site (e.g., Navajo Nation) where the cultural background of the subject population differs substantially from that of Pittsburgh and its surrounding communities?
  - \* No

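### The Aim 2 response model, as specified, cannot show who benefits over placebo; it admits on-treatment predictors that overlap the outcome, and manometry done before study drug is listed as a secondary end point

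*Combined protocol and SAP*

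**What the plan says.** - **The question.** CS2.1, after describing the function tests and questionnaires: "We will use this information to try to predict which groups of patients benefitted from the intervention". Section 2.6 (Research Plan) puts it more loosely, as factors that predict treatment response, and places it among the secondary analyses.
- **The model.** Section 2.18: "We will use logistic regression to determine the factors that predict treatment responses". Nothing more is specified, except that 2.18 applies a 0.05 threshold to every analysis.
- **The response.** Section 1.2, Aim 1: "We will define an adequate treatment response as greater than a 30% reduction in symptom severity using an intention-to-treat analysis".
- **The predictors.** Section 1.2, Aim 2 collects the "assessed severity of baseline and treatment-associated anorectal dysfunction", quality-of-life impact, daily diaries, anorectal testing and compliance, and then says: "All of these measures will be used to explore factors that are associated with treatment response".
- **Manometry.** Section 2.6 (Phase 2) describes a single routine test; patients obtain study drug at the end of that visit. Section 2.17 lists the test as secondary end point 8.
- **Expected placebo response.** Section 5.12 expects most patients, including those on placebo, to feel some improvement, because everyone is advised on treatment to alter stool form.

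**The concern.** Benefit from an intervention in a placebo-controlled trial is a difference between arms. Asking which groups benefit means asking whether that difference varies with a baseline factor, so the model needs an arm-by-factor term. Without one, a factor that marks good prognosis on either treatment can be reported, through the abstract's wording and the 0.05 threshold, as identifying the patients the suppository helps. Because 5.12 itself expects improvement on placebo, the two questions cannot be assumed to coincide.

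Two further problems follow from the text. Measures taken during treatment can appear predictive because they overlap the outcome. And a test done only before study drug is obtained cannot respond to the drug, so a between-arm comparison of it would show only baseline balance. What is at stake is how the Aim 2 results are read.

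**Working it through.** **1. The plan's own figure.** Inputs from 2.18 and 3.12: difference 3 points, SD 4, two-sided alpha 0.05, power 0.80. Per arm: 2 × (1.96 + 0.8416)² × 4² / 3² = 27.9, so 28. Total 56; 56 / 0.80 = 70 enrolled. This reproduces. It sizes the between-arm comparison; no figure is given for Aim 2.

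**2. What each reading of the model estimates.** Let A1 and A0 be the response rates on bisacodyl with and without a factor, and P1 and P0 those on placebo.

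- Bisacodyl arm only: A1 − A0.
- Both arms pooled 1:1, factor balanced: the average of (A1 − A0) and (P1 − P0).
- Who benefits over placebo: (A1 − P1) − (A0 − P0).

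Illustration with assumed rates, since the documents give none: P0 = 20%, P1 = 40%, A0 = 40%, A1 = 60%.

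- Bisacodyl only: 60 − 40 = 20 points.
- Pooled: 50 − 30 = 20 points.
- Benefit: 60 − 40 = 20 points with the factor and 40 − 20 = 20 points without it, a difference of 0.

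The factor predicts response under both readings, yet on this scale it says nothing about who benefits. Adding arm as a covariate does not change that; only the interaction addresses it.

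**3. Overlap of on-treatment severity with response.** Response is (baseline − week 4) / baseline > 0.30, that is, week 4 < 0.70 × baseline. At an assumed baseline of 7, response means a week-4 rating below 4.9. If treatment-associated severity is that rating, then given baseline it determines the outcome. If it is a symptom questionnaire repeated at the same Phase 3 visit, it is a parallel measure of the same state. The rating asks about the past 2 weeks, so the later diary pages cover the same days. The overlap is partial or complete depending on the measure; the plan does not say which is meant.

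**4. Manometry against the timeline.** Section 2.6: one test at Phase 2; study drug obtained at the end of that visit; no repeat at Phase 3. Section 2.17: secondary end point 8. Section 1.2, Aim 2: an explanatory factor. Only the last use fits the timeline.

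**5. What an interaction analysis could deliver.** On the change score, for which the plan gives SDs (4 assumed, about 2.5 from similar studies), with two equal subgroups (assumed) and 35 per arm:

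SE = SD × √(2/17.5 + 2/17.5) = SD × 0.478.

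| SD | SE | 3 / SE | Power (noncentral t, 66 df) | 95% CI half-width |
|---|---|---|---|---|
| 4 | 1.91 | 1.57 | 0.34 | 3.8 points |
| 2.5 | 1.20 | 2.51 | 0.70 | 2.4 points |

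If only 56 patients contribute, power is 0.28 and 0.60.

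On the responder scale, with 17.5 patients per arm-by-factor cell and no factor effect, the variance of the log ratio of odds ratios is the sum of 1 / [17.5 p(1 − p)] over the four cells.

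- Assumed 20% v 40%: 2 × 0.357 + 2 × 0.238 = 1.19; half-width 1.96 × 1.09 = 2.14; a factor of about 8.5 each way.
- Assumed 40% v 60%: 4 × 0.238 = 0.95; half-width 1.96 × 0.976 = 1.91; a factor of about 6.8 each way.

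**The case against.** The strongest reply is that this is a modest exploratory aim. The abstract says only that the study will try, Aim 2 says explore, and 2.6 calls the analysis secondary. A response model is what 1.2 and 2.6 ask for, and at this size an interaction analysis would rarely identify anyone. All of that stands. It limits the weight of the point, but it does not make a response model an answer to the abstract's question, nor on-treatment severity a sound predictor.

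Some stronger readings are tempting and are not supported:

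- **That the plan commits to a model pooled over arms.** Section 2.18 neither includes nor excludes arm, and treatment response could mean response within the bisacodyl arm. The point holds under either reading.
- **That the model has a high false-positive rate.** With assumed response rates and a purely prognostic factor, a factor-only model will flag it far more often than an interaction test does. That is legitimate power for a different question, not an error rate.
- **That compliance will be distorted by withdrawals.** Section 5.16 counts patients who withdraw after Phase 1 as non-responders, and Aim 2 says "Enrolled patients that complete the study will be assessed for study medication compliance". But no passage assigns withdrawals a compliance value. If Aim 2 is followed, they drop out of that analysis, and simulation with 14 of 70 withdrawn and compliance unrelated to response flags it in only 2–4% of trials. The objection to compliance as a predictor is that it arises after randomization.

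It is also fair to say that manometry is a labelling slip: the 2.17 list repeats the study-measures list in 2.6. It still needs correcting.

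**Conclusion.** The point holds as one of specification and interpretation. The abstract's question and the only stated model do not match; the literal predictor list includes measures that overlap the outcome; and one listed secondary end point cannot be affected by treatment. These findings rest on the text alone.

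The size of any misreading cannot be stated, because the documents give no response rates, factor list or analysis population. The precision figures assume equal subgroups, full data on 70 patients and the plan's SDs, or the response rates shown; unequal subgroups would do worse. A reader might infer that the trial's main result is in doubt. It is not: the between-arm comparison uses none of these models. The correction is worth making before Aim 2 is analysed, but it does not bear on whether the trial can proceed.

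**What to change.** 1. **Predictors (2.18 and Aim 2).** Limit them to variables measured before study drug: baseline severity and symptom questionnaires, the baseline diary and manometry. Describe on-treatment severity, on-treatment diaries and compliance by arm instead. Baseline severity is the denominator of the response, so its main effect should not be read simply as prognosis.
2. **Question (2.18 and CS2.1).** Choose one:
   - *Who benefits over placebo.* Fit arm, one baseline factor and arm-by-factor, for a short named list. Report interaction estimates with 95% CIs as exploratory, with no 0.05 claim. Fix the list before the first Phase 3 debriefing, since 2.6 reveals allocation patient by patient; if debriefing has begun, fix it before outcomes are tabulated by arm. A penalized fit for two-level factors is optional.
   - *Who improves.* State the population (both arms with arm as a covariate, or the bisacodyl arm only) and reword CS2.1 so that it no longer refers to who benefitted from the intervention.
3. **Manometry (2.17).** Move item 8 from the secondary end points to the baseline covariates.

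Cost: wording only, with no new data or visits. The first option under item 2 brings wide intervals; the second avoids them but gives up the claim about who benefits.

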3.8 Does this research study involve neonates of uncertain viability or nonviable neonates?

\* No

[reviewer notes¬]

- 3.9 Fetal Tissues: Does this research involve the use of fetal tissues or organs?
  - \* No

[reviewer notes¬]
--->

3.10 What is the total number of subjects to be studied at this site, including subjects to be screened for eligibility?

Note: The number below is calculated by summing the data entered in question 3.11. Any additions or changes to the values entered in 3.11 will be reflected in 3.10.

- \* 400
- 3.11 Identify each of the disease or condition specific subgroups (include healthy volunteers, if applicable) that will be studied.

Click on the "Add" button and specify for each subgroup:

- 1) how many subjects will undergo research related procedures at this site; and
- 2) if applicable, how many subjects will be required to undergo screening procedures (e.g., blood work, EKG, x-rays, etc.) to establish eligibility. Do Not include subjects who will undergo preliminary telephone screening.

\*

Subgroup	Number to undergo research procedures	Number to undergo screening procedures
View MS patients	70	400

- 3.12 Provide a statistical justification for the total number of subjects to be enrolled into this research study at the multicenter sites or this site.
  - \* Described below:

The primary outcome measure is the group mean difference in subjective severity ratings of bowel symptoms using a 10 point scale. It is generally regarded that a 3-point reduction represents a clinically meaningful change using such a scale, and similar

Section: Section 3 - Human Subjects

research studies using patient-reported outcomes have reported standard deviations ranging around ~2.5 points on a 10 point scale. However, we do not have baseline data in this population to estimate variance, and thus we took a conservative estimate with an expected standard deviation of 4 points. Given these assumptions, we will need 28 patients in each study arm to detect at least a 3 point reduction in symptom severity, with a power of 0.80, alpha=P<0.05 in a two-tailed analysis.

Thus, the study is adequately powered if enrollment reaches 56 patients. However, to ensure adequate numbers in an intention-to-treat analysis, we will plan for a ~20% patient drop-out rate. Therefore, we will aim to enroll 70 patients in total.

[reviewer notes¬]

3.13 Inclusion Criteria: List the specific criteria for inclusion of potential subjects.

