If the subject withdraws from the study after having passed Phase 1 (i.e. baseline measures of bowel dysfunction and quality of life), we would keep the data for an "intention-to-treat" analysis (with the assumption of an non-response). If a subject has not completed Phase 1, then the research data will be destroyed.

**5.17** Following the required data retention period, describe the procedures utilized to protect subject confidentiality. (e.g., destruction of research records; removal of identifiers; destruction of linkage code information; secured long-term retention)

We will destroy primary research records with any identifiers, but may opt to retain deidentified electronic data on a secured server for future re-analysis. Per University of Pittsburgh guidelines, research records will be archived for a minimum of seven years after final reporting or publication of a project.

Section: Section 6 - Costs and Payments

[reviewer notes-]

6.1 Will research subjects or their insurance providers be charged for any of the procedures (e.g., screening procedures, research procedures, follow-up procedures) performed for the purpose of this research study?

Yes; charges will be billed only for procedures performed as part of the subject's routine clinical care as addressed in question 2.9

[reviewer notes-]

6.2 Will subjects be compensated in any way for their participation in this research study?

\* No

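### Aim 2 looks for predictors only through the >30% response cut; a full-scale model of the same rating would be more efficient at the cost of one sentence

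*Combined protocol and SAP*

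**What the plan says.** Section 2.18 gives one sentence to the predictor analysis: "We will use logistic regression to determine the factors that predict treatment responses". It does not say which outcome is modelled, but section 1.2, Aim 1, supplies the only definition of response: "We will define an adequate treatment response as greater than a 30% reduction in symptom severity using an intention-to-treat analysis". Sections 2.6 and 2.17 repeat the 30% threshold as the primary end point. Aim 2 is worded as exploration: "All of these measures will be used to explore factors that are associated with treatment response".

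The same item also appears on its full scale. Aim 1 names the change in the rating as the primary endpoint, and section 3.12 bases the sample size on it: "The primary outcome measure is the group mean difference in subjective severity ratings of bowel symptoms using a 10 point scale".

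On withdrawals after Phase 1, section 5.16 says: "we would keep the data for an 'intention-to-treat' analysis (with the assumption of an non-response". On significance, section 2.18 says: "A p<0.05 will be used as the threshold for statistical significance in all cases". No power, factor effect or expected response rate is given for Aim 2.

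**The concern.** A yes/no cut scores a 31% fall and a 90% fall as the same result, and no change and a worsening as the same result. With 56 to 70 patients, and a sample size set by Aim 1, discarding that detail makes a real predictor (a manometry measure, for example) easier to miss. The plan gives no reason for using the cut in the predictor analysis, although the full rating is already collected at baseline and at week 4.

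There is a second, conditional issue. If the section 5.16 rule also governs this regression, withdrawals enter as non-responders whatever their rating. A factor related to leaving the study could then look like a predictor of non-response.

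**Working it through.** **Inputs from the plan.** Difference 3 points, SD 4 (about 2.5 in similar studies), two-sided alpha 0.05, power 0.80, 28 per arm, about 20% drop-out, 70 enrolled (sections 2.18 and 3.12).

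**The plan's own figure.** n per arm = 2(1.960 + 0.842)² × 4² / 3² = 2 × 7.85 × 16/9 = 27.9, so 28. Then 56/0.8 = 70. Both reproduce, but they concern the arm comparison and not Aim 2.

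**Closed-form check of the cut (assumed inputs).** For a response rate p, a cut of a normal outcome keeps φ(z_p)² / [p(1−p)] of the information.
- p = 0.5: 0.3989²/0.25 = 0.637.
- p = 0.4: 0.3863²/0.24 = 0.622.

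Take one factor with correlation r = 0.3 to the outcome. Full-scale power is Φ(atanh(r)√(n−3) − 1.960). With the cut, the first term is multiplied by √0.637 = 0.798.
- n = 56: 0.3095 × 7.280 = 2.253, so Φ(0.293) = 0.62. With the cut, 1.798, so Φ(−0.162) = 0.44. Loss about 18 points.
- n = 70: 0.3095 × 8.185 = 2.533, so Φ(0.573) = 0.72. With the cut, 2.022, so Φ(0.062) = 0.52. Loss about 19 points.

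**Simulation on the 1-10 rating (assumed inputs).** Baseline mean 7, SD 1.5. Ratings are rounded and kept within 1-10. Residual SD is 2.5 or 4. Placebo change is 0 with an arm effect of 3, or 1 with an arm effect of 1.5. The factor shifts the change by 0.3 or 0.4 residual SD per SD of the factor. Response runs at about 40-46%. Both models include arm and baseline rating; the linear model uses the t-test and the logistic model the likelihood-ratio test.

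| n | Factor effect | Linear power | Logistic power |
|---|---|---|---|
| 56 | 0.3 SD | 0.48-0.53 | 0.37-0.42 |
| 70 | 0.3 SD | 0.59-0.64 | 0.44-0.48 |
| 56 | 0.4 SD | 0.73-0.79 | 0.56-0.63 |
| 70 | 0.4 SD | 0.83-0.86 | 0.66-0.72 |

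Over repeat runs the loss lies between about 9 and 22 points. With no factor effect, rejection is about 4-6% (linear) and 5-7% (logistic), so the gain is not bought with false positives.

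**Arm-by-factor term.** With the factor acting in the active arm only, at 0.3 or 0.4 SD, power was 0.15-0.31 (linear) and 0.14-0.25 (logistic). A second set of runs at 0.4 SD gave 0.19-0.33 over the two models. Across all runs the gain is roughly 0 to 13 points.

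**Withdrawals, if section 5.16 applies here.** 0.20 × 70 = 14 outcomes would be assigned and not observed. All figures below are at 0.4 SD.
- *Random withdrawal:* linear 0.72-0.78 on the observed ratings, logistic 0.45-0.55 on all 70, a gap of about 17-27 points. In one cell (SD 4, placebo change 0, arm effect 3) the gap is 0.83 − 0.71 = 12 points with no withdrawals and 0.75 − 0.53 = 22 points with them.
- *Non-responders leave more often:* assume 35% of non-responders and 3% of responders leave. At 44% response this is 0.56 × 0.35 + 0.44 × 0.03 = 0.21 overall. Linear 0.74-0.77, logistic 0.66-0.69, a gap of about 4-12 points.

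**The case against.** **The logistic model is coherent.** Sections 2.6 and 2.17 declare the >30% improvement as the primary end point, and modelling predictors of a declared end point is a natural choice. This stands, and it is why the point is about efficiency and not error. That Aim 1 and section 3.12 describe a continuous primary outcome instead is a separate inconsistency.

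**The large figure answers the looser question.** The abstract (CS2.1) speaks of predicting which patient groups gained from the intervention. In a two-arm trial that is an arm-by-factor question. A reader might infer that the cut costs 9 to 22 points of the trial's ability to say who benefits from bisacodyl. It does not: for that term the difference is roughly 0 to 13 points, and neither model finds such a factor reliably. The larger range applies to the wider wording of Aim 2, factors associated with response.

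**The withdrawal issue is conditional.** A reader might infer that 14 of the 70 Aim 2 outcomes will be imputed. Section 5.16 ties the rule to the intention-to-treat analysis, and nothing says outright that it governs the Aim 2 regression. Fourteen is also a ceiling. Patients who leave between Phase 1 and the Phase 2 testing have no manometry values, so they enter neither model for those factors.

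**The linear model has limits.** It uses completers only. It targets points and not the relative fall that the plan calls response. It also needs care when the baseline rating is itself the candidate factor. All three are fair, and they are reasons to keep the logistic model alongside it.

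**Conclusion.** The point holds as a cheap improvement. Using the cut as the sole Aim 2 outcome gives up about 9-22 points of power per factor for a pooled association. That range assumes one factor at a time, an effect of 0.3-0.4 residual SD, a roughly linear relation, 56-70 patients and about 40-46% response. None of the factor-effect, baseline or response-rate inputs comes from the documents, and the range moves with them.

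The documents do not support reading this as a wrong figure, a failed power claim or a threat to the primary comparison. Aim 2 promises exploration and states no power, and the sample-size calculation concerns the arm comparison only. The size of any extra loss from withdrawals cannot be fixed from the plan, because it depends on whether section 5.16 applies and on why patients leave.

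**What to change.** In section 2.18, replace the logistic regression sentence with:

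> *Factors associated with treatment response will be examined by linear regression of the week-4 1-10 severity rating on the factor, adjusted for baseline rating and study arm, in patients with an observed week-4 rating; logistic regression of the >30% response will be reported as supportive.*

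Add two short statements:
- When the baseline rating is itself the factor, its coefficient is read as association with the week-4 score and not as response. For that factor, rely on the supportive logistic model or a baseline-by-arm term.
- The observed-case model assumes that patients who withdraw resemble similar patients who were observed. Say also whether the section 5.16 non-response rule applies to the supportive logistic model.

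The cost is a few lines of text, with no new data, visits or patients. The main Aim 2 results would be in scale points and not odds ratios, though the odds ratios stay in the supportive table. The completers-only assumption replaces the non-response assumption and would be wrong if leaving depends on outcome in ways that baseline, arm and the factor do not capture.

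### Section 2.18 leaves the Bonferroni family undefined; read literally it corrects a primary t-test that was powered at an uncorrected 0.05

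*Combined protocol and SAP*

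**What the plan says.** Section 2.18 assigns Fisher's exact test to categorical data and mentions no correction there. For the rest it says: "Continuous data will be analyzed using Student's t-tests to detect differences in group means, with Bonferroni correction for multiple comparisons". A separate sentence then reads: "A p<0.05 will be used as the threshold for statistical significance in all cases". The section does not say which comparisons form the family, how many there are, whether the primary is one of them, or whether the p-value meant is raw or adjusted.

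Section 3.12 describes the primary as continuous: "The primary outcome measure is the group mean difference in subjective severity ratings of bowel symptoms using a 10 point scale". Its sample-size statement is that "we will need 28 patients in each study arm to detect at least a 3 point reduction in symptom severity". That calculation is two-sided at 0.05 for 80% power, and it makes no allowance for a correction.

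The primary is not described the same way throughout. Sections 2.6 (Research Plan) and 2.17 make it a yes/no response, an improvement of more than 30%. Aim 1 in section 1.2 calls it the change in rating and gives the 30% figure as the definition of response.

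The secondary endpoint list in section 2.17 has eight numbered items. The diary item alone yields several measures. Two others, study-drug compliance and anorectal manometry, are not post-treatment efficacy outcomes: section 2.6 describes manometry as a single test in Phase 2, and study drug is handed out at the end of that visit.

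**The concern.** The correction in section 2.18 is triggered by the type of data, not by the role of the outcome. A mean-difference primary is therefore inside it on a literal reading, and a responder primary is outside it. Settling which primary applies would also settle, as a side effect, which significance level it faces.

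Two things are at stake. If the primary is corrected, the trial does not have its stated power at its own planning assumptions. If raw p-values are compared with 0.05 throughout, the secondary claims have no familywise error control. A raw p of 0.02 on the primary, or on a quality-of-life score, would be significant under one reading and not under another. Nothing in the text stops that reading from being chosen after the data are seen.

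**Working it through.** **Inputs.** Difference 3 points, two-sided alpha 0.05, power 0.80 and 28 per arm (section 3.12). SD 4 (sections 2.18 and 3.12: "we took a conservative estimate with an expected standard deviation of 4 points"). SD of about 2.5 in similar studies (section 2.18: "similar research studies using patient-reported outcomes have reported standard deviations ranging around ~2.5 points"). Allocation 1:1 (section 1.2); 56 evaluable and 70 enrolled (section 3.12). The number of comparisons m is not given, so m = 2, 6, 8 and 10 are assumptions.

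**Step 1: reproduce the plan's figure.** n per arm = 2 × (z for 0.975 + z for 0.80)² × SD² / difference² = 2 × (1.960 + 0.842)² × 16 / 9 = 27.9, rounded up to 28. Power at 28 per arm by the same normal approximation is 0.801. The t-based calculation gives 0.787 and n = 28.9. A one-sided test would need 22. So the 28 corresponds to an uncorrected two-sided 0.05. Allowing for 20% drop-out, 56 / 0.80 = 70, as stated.

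**Step 2: put the primary t-test in a Bonferroni family of m.** Each test is run at 0.05/m. Power comes from the noncentral t distribution with standardised difference 3/4 = 0.75 (or 3/2.5 = 1.2) and noncentrality equal to that difference × √(n/2).

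| m (assumed) | alpha per test | 28 per arm, SD 4 | 35 per arm, SD 4 | 28 per arm, SD 2.5 |
|---|---|---|---|---|
| 1 | 0.05 | 0.787 | 0.871 | 0.993 |
| 2 | 0.025 | 0.691 | 0.799 | 0.984 |
| 6 | 0.00833 | 0.531 | 0.662 | 0.956 |
| 8 | 0.00625 | 0.490 | 0.624 | 0.945 |
| 10 | 0.005 | 0.459 | 0.595 | 0.935 |

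The 35-per-arm column analyses all 70 and ignores any dilution from withdrawals, whom section 5.16 counts as non-responders.

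To regain 0.80 at SD 4 with the primary in the family, the normal approximation needs 34 per arm for m = 2 and 48 for m = 10. After 20% drop-out that means enrolling 68/0.80 = 85 and 96/0.80 = 120.

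**Step 3: the responder reading.** A yes/no primary goes to Fisher's exact test, to which section 2.18 attaches no correction. Its alpha stays at 0.05 and the loss in Step 2 does not arise. The plan's power figure is for a difference in means, so it does not describe the power of that analysis.

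**Step 4: the raw-p reading for secondaries.** With independent tests and no true effects, the chance of at least one p<0.05 is 1 − 0.95^m: 1 − 0.95⁶ = 0.265 and 1 − 0.95⁸ = 0.337. At an assumed correlation of 0.4, simulation (40,000 runs, t-tests, 28 per arm) gives about 0.23 for six tests and 0.28 for eight.

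**Step 5: Holm against Bonferroni.** Assuming six secondary outcomes, standardised effect 0.6 in each, correlation 0.4 and 28 per arm, simulated average power per outcome with t-tests is about 39% for Holm and 32% for Bonferroni. None of these three assumptions comes from the documents.

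**The case against.** A reader might infer that section 2.18 contradicts itself. It does not: multiplying each p-value by m and comparing the result with 0.05 satisfies both the Bonferroni clause and the universal threshold. That objection stands, and it limits the point to under-specification. It still leaves open which tests are in the family.

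A reader might also infer that the trial is underpowered. The documents do not establish that. The correction is "with Bonferroni correction for multiple comparisons", and a single designated primary is conventionally not one of several. The sample size at an uncorrected 0.05 suggests the authors intended just that. The loss needs a mean-difference primary, inside the family, at an SD that the plan itself calls conservative. At SD 2.5 power stays at 0.935 or more up to ten tests, and with all 70 analysed a family of two keeps about 0.80. All of this stands. Against it, SD 4 is the plan's own design value, chosen because it had no baseline data, and nothing in the text places the primary outside the correction.

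Finally, Bonferroni is a valid method, and moving to Holm does not resolve any ambiguity. That is fair. Defining the family is the essential step; Holm is an inexpensive gain made in the same edit.

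**Conclusion.** The point holds as a conditional one. The multiplicity rule does not define its family, and its literal wording covers a mean-difference primary that was powered without correction. On that reading, at SD 4 and 28 per arm, power falls from 0.79 to 0.69, 0.53 or 0.49 for assumed families of 2, 6 or 8. With all 70 analysed the figures are 0.80, 0.66 and 0.62. If the primary is the responder endpoint, or is tested outside the family, there is no loss from this source. On the raw-p reading, 6 to 8 secondary tests carry a 26% to 34% chance of a false positive if independent, and about 23% to 28% at an assumed correlation of 0.4. The text should be changed before unblinding because the readings can give different verdicts on the same data.

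**What to change.** Three edits to section 2.18:

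1. State that the single primary comparison is tested alone at two-sided 0.05, outside any correction. Settle in the same sentence whether it is the mean difference or the responder endpoint, and align sections 1.2, 2.6, 2.17 and 3.12. The alpha then matches the sample-size calculation and, for the mean difference, 28 per arm stands. If the responder endpoint is chosen, its power needs its own calculation.
2. Replace Bonferroni with Holm over one named list of post-treatment secondary efficacy outcomes, continuous and categorical together, with adjusted p-values compared with 0.05. Leave baseline manometry and compliance off the list.
3. Replace the universal 0.05 sentence with one that says which p-values it applies to: the raw p for the primary and the Holm-adjusted p for listed secondaries. Report remaining comparisons with confidence intervals and no significance claim.

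The cost is a few sentences, with no added patients, visits or data under the mean-difference primary. Holm controls the same familywise error as Bonferroni and never rejects fewer hypotheses. Its one small drawback is that it has no simple matching simultaneous confidence intervals. If the primary is meant to stay in the family, the sample size must be redone at 0.05/m.
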